Table 2 Study Drug Starting Dose by Age Cohorta in the Core Phase and Extension Phase

Age Range (Years)	Study Drug Starting Dose (mg)	Formulation
	Cohort 1	
≥12 to <18 20 mg Once Daily Oral Tablet		
Cohort 2		
≥6 to <12	20 mg Once Daily	Oral Tablet
Cohort 3		
≥1 to <6	10 mg Once Daily	Capsule

a: Subject age at the time of randomization will be used. The starting dose of study drug may be revised after scheduled PK/PD and safety reviews (Section 5.1).

Table 3 Study Drug Dose Adjustments in the Core Phase and Extension Phase

Platelet Count (×10 ⁹ /L)	Dose Adjustment or Action
$<50\times10^9/L$ after at least 2 weeks of dosing.	 Increase 1 Dose Level per Table 4. Wait 2 weeks to assess the effects of this regimen and any subsequent dose adjustments.
>150×10 ⁹ /L to ≤250×10 ⁹ /L	 Decrease 1 Dose Level per Table 4. Wait 2 weeks to assess the effects of this regimen and any subsequent dose adjustments.
>250 ×10 ⁹ /L	 Stop study drug. Increase platelet monitoring to twice weekly. When platelet count is ≤100×10⁹/L, decrease 1 Dose Level per Table 4.
<30×10 ⁹ /L after 3 weeks of once daily dosing at the cohort defined maximum dose per Table 4.	Discontinue study drug.
Also see protocol stopping criteria in Section 5.3 and early termination criteria in Section 6.1.6.	
>250×10 ⁹ /L after 2 weeks of once weekly dosing for any age cohort	Discontinue study drug.

 Table 4
 Study Drug Dose Level Titration (Core and Extension)

Dose	Dose Level
Cohort 1 (≥12 to <18 Years) and Cohort 2 (≥6 to <12 Years) Dosed with Oral Tablet	
40 mg Once Daily	6
40 mg Three Times a Week AND 20 mg on the Four Remaining Days of Each Week	5
20 mg Once Daily ^a	4
20 mg Three Times a Week	3
20 mg Twice a Week	2
20 mg Once Weekly	1
Cohort 3 (≥1 to <6 Years) Dosed with Powder for Oral Suspension	
20 mg Once Daily	6
20 mg Three Times a Week AND 10 mg on the Four Remaining Days of Each Week	5
10 mg Once Daily ^a	4
10 mg Three Times a Week	3
10 mg Twice a Week	2
10 mg Once Weekly	1

a: Subject age at the time of randomization will be used. Initial dose regimen based on modeling and simulation. Actual initial dose in Cohort 2 and Cohort 3 may be modified after modeling is completed using data from the previous cohort.

To ensure accuracy of the predictions, PK, platelet response, and safety data will be reviewed by the Sponsor, or the Sponsor's unblinded designee, as described in Section 5.1 and if necessary, adjustments of the dose level may be made following these data reviews.

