5.3 Stopping Criteria

Subjects may be removed from the Core Phase and directly enrolled into the open-label Extension Phase due to a lack of treatment effect.

A lack of treatment effect will be defined as:

- Platelet count remains <30×10⁹/L after more than 3 weeks at the maximum dose of study drug per Table 4. Subjects may also be terminated from the Core Phase and directly enrolled into the Extension Phase after 7 days of therapy at the maximum dose if they have dangerously low platelet counts (in the opinion of the Investigator), or
- Subjects who require rescue therapy more than 3 times or continuous rescue therapy for more than 3 weeks (Section 8.6).

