6.3.2 Early Termination

A subject may be early terminated from the Core Phase or the Extension Phase for any of the following reasons:

- A platelet count $>250\times10^9$ /L after 2 weeks of once weekly dosing for any age cohort.
- Subject or the subject's LAR, as applicable, wishes to withdraw consent/assent for any reason.
- Subject non-compliance or unwillingness to comply with the procedures required by the protocol.
- Occurrence of any medical condition that exposes the subject to substantial risk and/or does not allow the subject to adhere to the requirements of the protocol.
- Any SAE, clinically significant AE, severe laboratory abnormality, intercurrent illness, or other medical condition which indicates to the Investigator that continued participation in the study is not in the best interest of the subject.
- Pregnancy.
- Requirement of a prohibited concomitant medication (Section 8).
- Investigator discretion.
- Sponsor request.
- Termination of the study by the Sponsor or a regulatory agency.

In addition, a subject may be early terminated from the Extension Phase if they have a platelet count $<30\times10^9/L$ after 3 weeks of once daily dosing at the cohort defined maximum dose.

Every effort should be made during the conduct of the study to limit the extent of missing data. Except for subjects who are being withdrawn from the Core Phase due to a lack of treatment effect (Section 5.3), subjects who prematurely discontinue the study drug should remain in the study for collection of data, unless the subject withdraws consent. If a subject is early terminated from the Core Phase of the study after the first dose of study drug, but prior to the end of the PK blood collection (Visit 12/Week 10), consideration should be given to collecting all remaining PK blood draws, if possible.

If a subject is early terminated from the study after randomization, the Early Termination procedures (Section 9.3) should be performed. Subjects withdrawn from the study after randomization will not be replaced, regardless of the reason for withdrawal.

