9.1.11 Visit 10 (Week 8; Day 57 ± 1 Day)

The following assessments will be performed during Visit 10:

- Perform WHO Bleeding Scale Assessment (Appendix C). The Investigator should ask the subject and/or the subject's parent/caregiver the following question: "Have you had any bleeding or bruising since I saw you last?". This assessment should be completed prior to other visit assessments.
- Collect weight.

- Perform abbreviated PE. The abbreviated PE will consist of the following: general appearance, head, neck, eyes, ears, nose, throat, chest, lungs, heart, abdomen, extremities, joints, lymph nodes, and neurology
- Collect vital signs (blood pressure, heart rate, and temperature). Vital signs should be taken after sitting for 5 minutes, whenever possible, and prior to any blood draws.
- Collect blood for clinical laboratory tests (e.g., serum chemistry, hematology [Table 7]).
- Collect blood for platelet count (local laboratory) and assess need for study drug dose titration per Table 3.
- Collect blood for sparse PK sample (Section 9.6) and record date/time of the last dose of study drug in the eCRF.
- Perform urine or serum pregnancy test for female subjects of childbearing potential. The pregnancy test may be performed locally.
- Retrieve unused study drug and record compliance in the eCRF.
- Review study drug administration and Dosing Diary completion with the subject and/or the subject's caregiver.
- Dispense new Dosing Diary for the subject to take home with instructions for completion.
- Dispense 1-month supply of study drug for the subject to take at-home with instructions for administration.
- Record any AEs.
- Review and record any concomitant medications, including any modifications to or new concomitant ITP medications.
- Discharge subject from clinic with instructions for when to return for Visit 11.

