11.2.2 Efficacy Analysis

All efficacy analyses will be conducted using the FAS, unless otherwise specified.

In order to satisfy the primary endpoint requirements of different regulatory agencies, 2 primary efficacy endpoints will be evaluated. Two separate SAPs will be developed to describe the statistical methodology for the analysis of each primary efficacy endpoint. In the first SAP, the endpoint described as "Primary Efficacy Endpoint" in Section 3.1 will be assessed as the primary efficacy endpoint, and the endpoint described as the "Alternative Primary Efficacy Endpoint" in Section 3.2 will be assessed as the first secondary efficacy endpoint. In the second SAP, the endpoint described as "Alternative Primary Efficacy Endpoint" in Section 3.2 will be assessed as the primary efficacy endpoint, and the endpoint described as the "Primary Efficacy Endpoint" in Section 3.1 will be

assessed as the first secondary efficacy endpoint. Both SAPs will evaluate the additional secondary efficacy endpoints described in Section 3.3.

For the efficacy evaluation of the platelet count responses, platelet counts assessed by local labs will be used. Platelet counts collected via the central lab will be used in the safety assessments of clinical laboratory tests.

Primary Efficacy Endpoint:

The primary efficacy endpoint is the durable platelet response as defined by the proportion of subjects achieving at least 6 out of 8 weekly platelet counts $\geq 50 \times 10^9 / L$ during the last 8 weeks of the 12 week Treatment Period in the Core Phase, in the absence of rescue medication. The null hypothesis is that the treatment effect of avatrombopag is the same as that of placebo. The alternative hypothesis is that the treatment effect of avatrombopag is different than that of placebo.

The primary efficacy endpoint will be tested between avatrombopag and placebo using the Cochran-Mantel-Haenszel 2-sided test at α =0.05, adjusting for age cohort and Baseline platelet count (\leq 15×10⁹/L vs >15×10⁹/L), or the Fisher's exact test, when data is sparse. In addition, the numbers and percentages of responders in each treatment group, the associated 95% confidence intervals (CI), and the 95% CI for the difference between avatrombopag and placebo will be summarized. The primary analysis will be performed based on the FAS and repeated on the PPS as a supportive analysis. Other sensitivity analyses of the primary efficacy endpoint may be performed as appropriate.

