4. DEFINITIONS AND CONVENTIONS FOR DATA HANDLING

4.1 Study Periods

Study periods are defined as follows:

Screening Period: Starting the day of signature of informed consent up to and including the day before randomization. For subjects who are not randomized, the screening period will end on the day the subject is determined to be a screen failure.

Randomized Control Period / **Core Phase**: Starting the day of randomization up to Visit 14 or the day of study drug discontinuation.

Follow-up Period in Core Phase: Starting the day after last dose of study drug in the Core Phase up to 30 days (±7 days) following the last dose of study drug in the Core Phase (only for subjects not entering the open label extension period).

Open Label Extension Period: Starting the day of Visit E-1/Day 1 to early termination or end of study. Visit 14 and Visit E-1 occur on the same day, and as a result are part of both the Randomized Control Period and the Open Label Extension Period.

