7.4 Efficacy Analysis

Unless otherwise stated, all primary and secondary efficacy endpoints defined in Section 3.2.1 will be analyzed for the FAS and PPS.

For the efficacy evaluation of the platelet count responses, platelet counts assessed by local labs will be used. Platelet counts collected via the central lab will be used in the safety assessments of

clinical laboratory tests.

The methods used for efficacy analysis for the Core Phase are summarized in Error! Reference source not found.3. All Cochran-Mantel-Haenzel (CMH) tests at alpha=0.05 within each age cohort will be performed adjusting for baseline platelet count category ($\leq 15 \times 10^9 / L \text{ vs} > 15 \times 10^9 / L$). For the CMH test in the overall group, the test will be performed adjusting for age cohort and baseline platelet count category. Fisher's exact test will be used if the number of durable platelet responders is spare in the strata (less than 3 in a specific subgroup). Durable platelet response with 2-sided 95% exact binomial (Clopper-Pearson) confidence interval (CI) will be provided. The difference in response rate (avatrombopag – placebo) with 2-sided 95% CI (Wald) will also be provided.

Subjects without sufficient data for the determination of response status (i.e., responder versus non-responder) will be treated as non-responders in the analysis.

For the primary efficacy endpoint determination, a subject must have remained in the Core phase through at least Week 10 (to have at least 6 weeks of platelet count data starting from week 5 to either week 12 if the subject completes the core phase or the last week if the subject prematurely terminates the core phase). If a subject terminates the Core phase prior to Week 10, they would be considered a non-responder for the primary efficacy endpoint.

Endpoint	Analysis Method
Primary Efficacy Endpoint	
Durable platelet response defined as proportion of subjects achieving at least 6 out of 8 weekly platelet counts $\geq 50 \times 10^9 / L$ during the last 8 weeks of the 12 week treatment period in the Core Phase in the absence of rescue medication. In the case of rescue medication being used, platelet count assessments from the start date of rescue medication up until 4 weeks after the end date of rescue medication will be excluded from analysis.	CMH test

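### Protocol Table 3 orders study drug stopped for a count <30×10⁹/L after 3 weeks at maximum dose without requiring persistence, while Section 5.3 makes Core removal optional and requires persistence; read literally, one dip can cost a durable response

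*Protocol*

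**What the plan says.** Platelet counts below are in units of 10⁹/L.

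- **Protocol Section 1.5.3, Table 3** (headed for Core and Extension). A count <30 "after 3 weeks of once daily dosing at the cohort defined maximum dose per Table 4" leads to one action: discontinue study drug. The row adds "Also see protocol stopping criteria in Section 5.3 and early termination criteria in Section 6.1.6". There is no Section 6.1.6; early termination is in Section 6.3.2.
- **Protocol Section 5.3.** Subjects *may* be moved from the Core Phase to the Extension for lack of treatment effect. The platelet criterion is "Platelet count remains <30×10⁹/L after more than 3 weeks at the maximum dose of study drug per Table 4". Removal is also possible after 7 days at maximum dose if the investigator judges the count dangerously low, or for repeated or continuous rescue.
- **Protocol Section 6.3.2.** The <30 after 3 weeks reason is listed for the Extension only, again as *may*. Apart from Core withdrawals for lack of effect, "subjects who prematurely discontinue the study drug should remain in the study for collection of data".
- **Visit instructions, Visits 4 to 13** (for example Section 9.1.11): "Collect blood for platelet count (local laboratory) and assess need for study drug dose titration per Table 3".
- **SAP Section 4.1.** The Core Phase is defined as "Starting the day of randomization up to Visit 14 or the day of study drug discontinuation".
- **SAP Section 7.4.** "If a subject terminates the Core phase prior to Week 10, they would be considered a non-responder for the primary efficacy endpoint".

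**The concern.** The Table 3 row and Section 5.3 address the same clinical situation but differ in three ways. On persistence, Table 3 is silent and Section 5.3 requires it. On duration, one says 3 weeks and the other more than 3 weeks. On force, one is an instruction and the other a permission.

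Sites are sent to Table 3 every week with a single local count in hand. A child at Dose Level 6 whose counts are mostly ≥50, but who dips below 30 once, meets the Table 3 row as written and does not meet the Section 5.3 platelet criterion.

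The primary endpoint is built to tolerate such a dip, since 2 of the 8 weekly counts may be below 50. Stopping the drug removes that tolerance. The child would lose a drug that was working, could be scored a non-responder, and would not literally qualify for the Extension. Section 6.2.1 asks for 12 weeks of Core treatment or discontinuation for lack of effect as defined in Section 5.3.

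**Working it through.** **1. The plan's own power figure.** Inputs from Protocol Section 11.3: 54 avatrombopag and 18 placebo, durable response 41.3% and 3.4%, Fisher's exact test, α = 0.05. Two-sidedness comes from Section 11.2.2: "The primary efficacy endpoint will be tested between avatrombopag and placebo using the Cochran-Mantel-Haenszel 2-sided test at α =0.05", with Fisher's test when data are sparse.

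Power = Σₓ Σᵧ Bin(x; 54, p_A) · Bin(y; 18, p_P) · 1{two-sided Fisher p ≤ 0.05}.

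With p_A = 0.413 and p_P = 0.034 this gives 94.5%, so the stated minimum of 90% is confirmed.

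**2. When the Table 3 row can first apply.** Scheduled visits fall on Day 1 + 7w for Week w. Tables 3 and 4 start at Level 4 and allow one step up every 2 weeks:
- Level 5 at the earliest on Day 15 and Level 6 on Day 29 (Week 4).
- 29 + 21 = Day 50, which is Week 7.
- If 3 weeks is read as strictly more than 21 days, the first visit is Week 8.

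**3. One dip, fastest titration.** Suppose one of the Week 5 to 12 counts is <30 and the other seven would be ≥50 on continued drug. If the child continues under Section 5.3, the score is 7 of 8: a responder. If the drug is stopped at the dip and the Core Phase ends that day (SAP Section 4.1), the qualifying counts are Weeks 5 to w−1, that is w−5 of them.

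| Dip at Week | Day | Counts ≥50 before stop (w−5) | Result under literal Table 3 |
|---|---|---|---|
| 5 or 6 | 36, 43 | – | row does not yet apply |
| 7 | 50 | 2 | non-responder (Core ends before Week 10) |
| 8 | 57 | 3 | non-responder (same) |
| 9 | 64 | 4 | non-responder (same) |
| 10 | 71 | 5 | non-responder (fewer than 6) |
| 11 | 78 | 6 | responder still possible |
| 12 | 85 | 7 | responder still possible |

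So 4 of the 8 possible dip weeks cost the response, or 3 of 8 on the strict reading of 3 weeks. Later escalation to Level 6 shortens the window further.

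**4. If off-drug counts are kept instead** (Protocol Section 6.3.2 rather than SAP Section 4.1). The child needs 6−(w−5) further counts ≥50 from the 12−w weeks left: 4 of 5, 3 of 4, 2 of 3 or 1 of 2 after a dip at Week 7, 8, 9 or 10. Non-response is then not certain, but those counts must be reached without drug.

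**5. Illustrative size.** Expected avatrombopag responders: 0.413 × 54 = 22.3. Expected placebo responders: 0.034 × 18 = 0.6. Losing k responders changes p_A to 0.413 − k/54, with placebo held at 3.4%.

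| k lost | p_A | Fisher power |
|---|---|---|
| 0 | 41.3% | 94.5% |
| 1 | 39.4% | 92.0% |
| 2 | 37.6% | 88.8% |
| 3 | 35.7% | 84.8% |

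The values of k are assumptions. The documents give no frequency of isolated dips.

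**The case against.** The strongest reply is that there is one rule, loosely drafted. Table 3 never says that one count is enough, and its row sends the reader to Section 5.3. The Amendment 1 rationale (Appendix E) says the Extension definition was brought into line with the Core definition, and paraphrases the latter without any word for persistence; the same amendment edited this Table 3 row. The visit text asks for a titration assessment and does not itself order a stop. Section 9.5 allows a repeat test for a suspected laboratory error or a transient condition such as clumped platelets. All of this stands. A reader might infer that Table 3 mandates stopping on a single count. The documents do not say so; that is only what a literal reading yields.

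What remains is that the row, taken alone, is an instruction with no persistence condition. The titration step that sites follow weekly names Table 3 and not Section 5.3, and repeat testing is allowed rather than required. Different sites could reasonably act differently.

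A reader might also put a rate on the loss, say 5%, 10% or 20% of responders, and quote power of 91.7%, 88.0% or 77.3%. No such rate is in the documents. Even if 5%, 10% or 20% of responders had one dip at a random week among Weeks 5 to 12, the 4-of-8 factor would reduce the loss to 2.5%, 5% or 10%, with power 93.2%, 91.7% or 88.0%. Only children at Level 6 for at least 3 weeks, at sites reading the row literally, are exposed, which lowers the loss again.

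Finally, Section 5.3 has its own exit without persistence (7 days, dangerously low count). Aligning the texts would therefore not guarantee that every such child continues.

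**Conclusion.** The inconsistency is real and can change a child's primary-endpoint result. Its consequence is conditional on four things: Level 6 for at least 3 weeks, an otherwise responding child, a single count <30 at Weeks 7 to 10, and a site that applies Table 3 literally. Non-response is certain only if SAP Section 4.1 is followed and off-drug counts are not used.

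The number of children affected is unknown and probably small. One lost responder leaves power above the stated 90%; two would take it just below (88.8%). These figures rest on the planning rates and on Fisher's test, which the sample size uses, rather than on the stratified primary test.

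A reader might infer a threat to the validity of a positive result. The documents do not support that. The rule applies to both blinded arms, and with 0.6 placebo responders expected the loss falls almost wholly on avatrombopag. It lowers the active rate and does not inflate Type I error. The case for correction rests on consistent conduct, an undiluted effect estimate, and not stopping an effective drug or leaving a child's Extension eligibility unclear.

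**What to change.** In the next protocol amendment:

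1. Reword the Table 3 row to the Section 5.3 criterion: the count remains <30×10⁹/L after more than 3 weeks at the maximum dose.
2. Define *remains*: confirmed at the next weekly visit, or by a stated number of consecutive weekly counts. The sponsor should set the number; the documents do not point to a particular one.
3. Use the same wording and the same force (mandatory or optional) in Table 3, Section 5.3 and Section 6.3.2.
4. State that a Core subject stopped under this row meets Section 5.3 and may enter the Extension.
5. Change the reference from Section 6.1.6 to Section 6.3.2.

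For children already treated, add to the SAP a listing of those stopped under this row who had any count ≥50×10⁹/L in the preceding 3 weeks, so that any effect on the primary endpoint can be seen.

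The cost is one table row, one definition, matching text in two sections, one cross-reference and one listing. Visits, data collection and sample size do not change. The downside is that a true non-responder may stay on drug about a week longer. The 7-day exit for dangerously low counts and rescue therapy remain available in that week.

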1.5.4 Extension Phase Dosing Regimen

Subjects who complete the 12 week Core Phase of the study, or who meet the stopping criteria as defined in Section 5.3 and are discontinued from the Core Phase, will be eligible to enter the open-label Extension Phase, if they continue to meet the inclusion criteria and do not meet any exclusion criteria for this phase of the study (Section 4.1.2).

In the Extension Phase of the study, subjects will receive open-label avatrombopag as either the film-coated oral tablet (20 mg per tablet) or as a capsule containing a powder for oral suspension (10 mg per capsule) which can be opened to sprinkle the contents into an appropriate vehicle. The formulation received should be recorded in the electronic case report form (eCRF). The appropriate Extension Phase starting dose of open-label avatrombopag should be determined based on the instructions below.

- If a subject entering the Extension Phase has a platelet count within the target range of ≥50×10⁹/L to ≤150×10⁹/L on their current dose of study drug, they may continue that dose of open-label avatrombopag when entering the Extension Phase.
- If a subject entering the Extension Phase has a platelet count <50×10⁹/L when entering the Extension Phase, the subject should be started on the dose of open-label avatrombopag listed in Table 2, based on the subject's age cohort.
- If a subject entering the Extension Phase has a platelet count >150×10⁹/L when entering the Extension Phase, the initial dose of open-label avatrombopag in the Extension Phase should be titrated down per the instructions in Table 4, based on the subject's platelet count, in order to maintain a platelet count between ≥50 to ≤150×10⁹/L.

Throughout the Extension Phase, the dose of open-label avatrombopag may be titrated up or down per the instructions in Table 4, based on the subject's platelet count, in order to maintain a platelet count between >50 to $<150\times10^9/L$.

If subjects in Cohort 3 require higher doses of avatrombopag than what is listed in Dose Level 6 in order to maintain a platelet count $\geq 50 \times 10^9 / L$, the appropriate dose may be discussed with the Sponsor Medical Monitor (Table 4). However, across all age cohorts, the maximum allowable dose of study drug is 40 mg daily and the dose should not be increased beyond what is in Dose Level 6 in Table 4 for Cohort 3 without approval from the Sponsor Medical Monitor. If two subjects in Cohort 3 require escalation above Dose Level 6, a protocol amendment must be implemented before any additional subjects will be permitted to escalate above Dose Level 6.

